4.6 Blinding/Unblinding

Not applicable.

4.7 Treatment Compliance

Treatment Adherence to the treatment regimen will be critical to the conduct of this study. Adherence will be evaluated by the investigative staff at every treatment visit (including telephone contact visits) through interviews with the subjects and through examination of returned medication. It is expected that site staff attempt to have subjects maintain 90% treatment compliance or greater. Subjects should be instructed to bring all unused study medication back in the original container to each visit. Site staff are required to review Dosing Diaries completed by the subject, and to reinforce their use.

4.8 Destruction of Study Drug

For this study, study drugs (those supplied by BMS or sourced by the investigator) such as partially used study drug containers, vials and syringes may be destroyed on site.

Any unused study drugs can only be destroyed after being inspected and reconciled by the responsible Study Monitor unless study drug containers must be immediately destroyed as required for safety, or to meet local regulations (eg, cytotoxics or biologics).

On-site destruction is allowed provided the following minimal standards are met:

- On-site disposal practices must not expose humans to risks from the drug
- On-site disposal practices and procedures are in agreement with applicable laws and regulations, including any special requirements for controlled or hazardous substances
- Written procedures for on-site disposal are available and followed. The procedures must be filed with the site's SOPs and a copy provided to BMS upon request

- Records are maintained that allow for traceability of each container, including the date disposed of, quantity disposed, and identification of the person disposing the containers. The method of disposal, ie, incinerator, licensed sanitary landfill, or licensed waste disposal vendor must be documented
- Accountability and disposal records are complete, up-to-date, and available for the Monitor to review throughout the clinical trial period

If conditions for destruction cannot be met the responsible Study Monitor will make arrangements for return of study drug.

It is the investigator's responsibility to arrange for disposal of all empty containers, provided that procedures for proper disposal have been established according to applicable federal, state, local, and institutional guidelines and procedures, and provided that appropriate records of disposal are kept.

4.9 Return of Study Drug

If study drug will not be destroyed upon completion or termination of the study, all unused and/or partially used study drug that was supplied by BMS must be returned to BMS. The return of study drug will be arranged by the responsible Study Monitor.

It is the investigator's responsibility to arrange for disposal of all empty containers, provided that procedures for proper disposal have been established according to applicable federal, state, local, and institutional guidelines and procedures, and provided that appropriate records of disposal are kept.

5 STUDY ASSESSMENTS AND PROCEDURES

5.1 Flow Chart/Time and Events Schedule

Table 5.1-1: Screening Procedural Outline (AI468048)

Procedure	Screening Visit (42-day screening period)	Notes
Eligibility Assessments		
Informed Consent	X	
Call IVRS to Enroll the subject; PID assigned	X	
Inclusion/Exclusion Criteria	X	
Medical History	X	Includes historical CDC Class C Events
Non-Laboratory Safety Assessments		
Full Physical Examination	X	See Section 5.3.1 for requirements
Vital Signs & Physical Measurements	X	See Section 5.3.1 for requirements
Pre-treatment events	X	Only CDC Class C events with onset during the Screening period
Serious Adverse Events Assessment	X	All SAEs that occur after the ICF has been signed should be reported
ECG	X	See Section 5.3.4 for requirements
Pregnancy Test	X	WOCBP For females under age 55, an FSH level must be on record to confirm she is not a WOCBP if pregnancy testing is not being performed. If positive urine, request serum hCG quant. on lab requisition.
Laboratory Assessments		
Fasting Chemistry and Lipid Panel	X	Fasting overnight
Hematology	X	
Urinalysis	X	
Plasma HIV-1 RNA	X	This is the confirmatory HIV-1 RNA (The first value is provided by the PI)

Table 5.1-1: Screening Procedural Outline (AI468048)

Procedure	Screening Visit (42-day screening period)	Notes
CD4+ and CD8+ T-cell count	X	
HBV Surface Antigen	X	
HCV Serology	X	
Urine toxicology (drugs of abuse)	X	Could aid in the selection of appropriate study candidates.
Pharmacodiagnostic (PDx) sample ^a	X	Plasma collection to be banked for potential future use in development of novel predictive assay(s)
Resistance Testing (HIV-1 Drug Resistance)		
PhenoSense GT Plus Integrase	X	Complete set of test results may take up to 4 weeks.
PhenoSense Gag	X	
Next Generation Seq. - Qs Gag	X	
Exploratory Resistance (HIV-1 Drug Resistance)	X	Molecular analysis at BMS WFD Discovery of baseline resistant samples and baseline sensitive controls in cases of subsequent on-treatment virologic failure

^a By definition, a pharmacodiagnostic sample (PDx) is a pre-treatment test to determine whether or not a patient is likely to respond to a drug (ie, a predictive test). Based on the results of clinical studies with BMS-955176, BMS may have to develop a PDx assay. Thus, PDx samples obtained at Screening in this study would be used for that sole purpose.

Table 5.1-2: Short-term Procedural Outline (AI468048)

Procedure	In-clinic Visit Day 1	In-Clinic Visit Optional Week 2 for Intensive PK (Day 12-16)	In-Clinic Visits Weeks 4, 8, 12, 16, 24, 32, 40, 48, 60, 72, 84, 96, and/or Early Termination (ET) (± 5 days)	Phone Visits Weeks 20, 28, 36, 44, 54, 66, 78, 90 (± 5 days)	Notes
Eligibility Assessments					
Inclusion/Exclusion Criteria	X				
Non-Laboratory Safety Assessments					
Full Physical Examination			WK 12, 24, 48, 96/ET		See Section 5.3.1 for requirements
Targeted Physical Examination	X		WK 4, 8, 16, 32, 40, 60, 72, 84		See Section 5.3.1 for requirements
Vital Signs & Physical Measurements	X		X		See Section 5.3.1 for requirements
Adherence Assessments			X	X	Including review of Dosing Diaries
Pre-treatment Events	X				See Table 5.1-1
Adverse Events Assessments	X	X	X		Serious and Non-serious AEs
Concomitant Medications	X	X	X		See Section 5.3.3
ECG	X		WK 4, 12, 24, 48, 96/ET		See Section 5.3.4 for requirements
Pregnancy Test	X	X	X		For females under age 55, an FSH level must be on record to confirm she is not a WOCBP if pregnancy testing is not being performed. If positive urine, request serum hCG quant. on lab requisition.

Table 5.1-2: Short-term Procedural Outline (AI468048)

Procedure	In-clinic Visit Day 1	In-Clinic Visit Optional Week 2 for Intensive PK (Day 12-16)	In-Clinic Visits Weeks 4, 8, 12, 16, 24, 32, 40, 48, 60, 72, 84, 96, and/or Early Termination (ET) (± 5 days)	Phone Visits Weeks 20, 28, 36, 44, 54, 66, 78, 90 (± 5 days)	Notes
Provide WOCBP with Home Pregnancy test kit(s) to be used during the in-clinic visit interval			WK 16, 24, 32, 40, 48, 60, 72, 84		Provide One Kit at Weeks 16 - 40 Provide Two Kits at Weeks 48 - 84 WOCBP subjects perform test Q4 weeks at home and report results to site.
Laboratory Assessments for Safety and Efficacy and Other Endpoints					
Fasting Chemistry	X		X		Fasting overnight
Fasting Lipid Panel	X		WK 4, 12, 24, 48, 96/ET		Fasting overnight
Hematology	X		X		
Urinalysis	X		X		
Fractional Excretion of Phosphorous (FePO4) (Urine creatinine and phosphorus, Serum creatinine and phosphorus)	X		WK 48 and 96/ET		
Plasma HIV-1 RNA	X	X	X		If collecting an HIV-1 RNA at an UNSCHEDULED visit, also collect samples for Resistance and Exploratory Resistance Testing
CD4 and CD8 T-cell counts	X		X		
HBV Surface Antigen			WK 48 and 96/ET		
HCV Serology			WK 48 and 96/ET		Positive HCV Ab will reflex to HCV RNA

Table 5.1-2: Short-term Procedural Outline (AI468048)

Procedure	In-clinic Visit Day 1	In-Clinic Visit Optional Week 2 for Intensive PK (Day 12-16)	In-Clinic Visits Weeks 4, 8, 12, 16, 24, 32, 40, 48, 60, 72, 84, 96, and/or Early Termination (ET) (± 5 days)	Phone Visits Weeks 20, 28, 36, 44, 54, 66, 78, 90 (± 5 days)	Notes
Resistance Testing (HIV-1 Drug Resistance)					
PhenoSense GT Plus Integrase	X		X		Samples stored and tested if needed (ie, analyses of subjects if deemed clinically relevant) See Section 5.4.2.2
PhenoSense Gag	X		X		
Next Generation Seq. - Qs Gag	X		X		
Exploratory Resistance (HIV-1 Drug Resistance)	X		X		Samples stored and tested retrospectively if needed (ie, exploratory analyses for subjects if deemed clinically relevant)
Intensive PK sample collection		X			Use of PK Tools for data collection recommended. See Section 5.5.1 for requirements
Sparse PK sample collection			WK 4, 8, 12, 16, 24		See Section 5.5.2 for requirements
Bone Biomarkers (PINP and CTX)	X		WK 12 and 24/ET		Serum collection
Renal Biomarkers (β 2-microglobulin and creatinine)	X		WK 48 and 96/ET		Urine collection
Backup Serum and Plasma Sample	X		X		Samples stored and tested if needed

Table 5.1-2: Short-term Procedural Outline (AI468048)

Procedure	In-clinic Visit Day 1	In-Clinic Visit Optional Week 2 for Intensive PK (Day 12-16)	In-Clinic Visits Weeks 4, 8, 12, 16, 24, 32, 40, 48, 60, 72, 84, 96, and/or Early Termination (ET) (± 5 days)	Phone Visits Weeks 20, 28, 36, 44, 54, 66, 78, 90 (± 5 days)	Notes
Outcomes Measures					
EQ-5D-3L Form	X		WK 12, 24, 32, 40, 48, 60, 72, 84, 96		Health Outcomes Questionnaire
FAHI Form	X		WK 12, 24, 32, 40, 48, 60, 72, 84, 96		Functional Assessment of HIV Infection
Clinical Drug Supply					
Call IVRS to Randomize	X				
Dispense Study Drug	X		X		There is no dispensation at Week 96 or ET.

5.1.1 *Retesting During Screening or Lead-in Period*

Retesting of laboratory parameters and/or other assessments within any single Screening or Lead-in period will be permitted (in addition to any parameters that require a confirmatory value). The Screening Period for this study is 42 days.

Any new result will override the previous result (ie, the most current result prior to Randomization) and is the value by which study inclusion will be assessed, as it represents the subject's most current, clinical state.

Laboratory parameters and/or assessments that are included in [Table 5.1-1](#), Screening Procedural Outline may be repeated in an effort to find all possible well-qualified subjects. Consultations with the Medical Monitor may be needed to identify whether repeat testing of any particular parameter is clinically relevant (eg, a previously failed inclusion criterion).

Rescreening is different than Retesting. Rescreening is the process of Re-enrollment and requires that all procedures be repeated in an entirely new screening period. Rescreening will also be allowed. If it is clinically reasonable, and upon Investigator assessment (and in consultation with the BMS Medical Monitor, if necessary), a subject may be rescreened multiple times during the entire course of the enrollment period. Therefore, subjects may be Rescreened, if, in the opinion of the Investigator, a current clinical outlook of the subjects seems favorable for study inclusion (and if the patient never received study medication in this trial).

The assigned patient identifier (PID) for the subject must be Screen Failed in the IVRS. A new call must be made to the IVRS for the assignment of a new PID for the subject, and all Screening parameters must be done again in reference to the new PID (See [Section 3.3.1](#), Inclusion Criteria 2f). Subject must also be re-consented with the new PID.

5.2 *Study Materials*

The sponsor will provide each investigative site with the following:

- BMS-955176 Investigator Brochure (IB) and any relevant safety addenda or updates
- Protocol and any Amendments to the Protocol
- Instructions for completing electronic Case Report Forms (eCRFs)
- Laboratory Manual from the central laboratory
- ECG Machines and manual
- IVRS Worksheets to complete when calling the IVRS center to enroll, randomize, and discontinue subjects
- Patient-reported Outcomes Questionnaires: EQ-5D-3L Health Outcome Questionnaire, FAHI (Functional Assessment of HIV Infection)
- PK Tools/Job Aids that may be used for detailed instruction about the PK visits, and as a comprehensive source for documents of date/times of dosing and blood sampling
- Dosing Diaries
 - Completion by subjects is required

- Should include daily dose of study medications administered by subject, modified or missed
- Site staff should review the diaries with the subject at each visit, and, in combination with detailed questioning, should be able to provide comprehensive information in the case report form, noting discrepancies in the subject's file. Dosing Diaries should be maintained in the subject's study file.

5.3 Safety Assessments

The investigative team should follow the protocol-specified schedule of safety-related measurements. Only data for the procedures and assessments specified should be submitted to BMS on the case report form. Additional procedures and assessments may be performed as part of standard of care, however, data for these assessments should remain in the subject's medical record and should not be submitted to BMS, unless specifically requested (ie, as part of an SAE).

5.3.1 *Vital Signs and Physical Examinations*

The schedule of vital signs, physical examinations, and targeted physical examinations is provided in [Section 5.1](#) (Flow Chart/Time and Events Schedule). Vital signs include heart rate, blood pressure, respiration rate, and temperature and should be measured after the subject has been sitting/resting for at least 5 minutes. Physical measurements include height and weight. Targeted physical examinations will include examination of the heart, lungs, skin, abdomen, any symptomatic organ system, and general appearance.

5.3.2 *Adverse Events*

Subjects will be closely monitored throughout the study for any new or ongoing HIV-related diagnoses ([Appendix 2](#)) and/or adverse events. CDC Class C events that occur from the Screening Visit through Day 1 (prior to dosing), will be recorded as Pre-treatment Events. All events that occur after dosing on Day 1 will be recorded on the appropriate Adverse Event eCRF. Additional information on Adverse Events is provided in [Section 6](#).

5.3.3 *Concomitant Medication Assessment*

All medications taken from the Screening Visit throughout the duration of the study will be reported. In addition, any prior therapy with antiretroviral drugs will be reported (See [Appendix 1](#) for Prohibited and Precautionary Therapies).

5.3.4 *Electrocardiograms*

The schedule of electrocardiograms (ECGs) is provided in Section 5.1 (Flow Chart/Time and Events Schedule). ECG machines will be provided by a central vendor who will also perform the read/interpretation of the output.

5.4 Efficacy Assessments

5.4.1 *Primary Efficacy Assessment*

The primary assessment for efficacy is HIV-1 RNA through Week 24.

5.4.1.1 Guidelines for Confirmatory Testing of Plasma HIV-1 RNA and Resistance testing

A confirmatory HIV-1 RNA viral load should be obtained when:

- HIV-1 RNA \geq 40 c/mL if prior suppression $<$ 40 c/mL, or
- $> 1 \log_{10}$ c/mL increase in HIV-1 RNA at anytime above nadir level where nadir is \geq 40 c/mL

All efforts should be made to collect this sample within 2-4 weeks from the collection of the original sample.

When collecting a blood sample for HIV-1 RNA testing at an Unscheduled visit, samples should also be collected for the sets of Resistance and Exploratory Resistance Tests, so that the samples are available should resistance testing be required or deemed necessary based on the result of the HIV-1 RNA test.

Table 5.4.1.1-1: Management of Detectable HIV-1 RNA, based on Confirmed (2-4 weeks from original sample) or Consecutive HIV-1 RNA Result^a

Day 1 through Week 24	
40 - 399 c/mL	Reinforce Adherence
\geq 400 c/mL	Consider the need for resistance testing, in consultation with BMS Medical Monitor. Consider possible discontinuation of subject, in consultation with BMS Medical Monitor, and/or reinforce adherence.
After Week 24 through Week 48	
40 - 399 c/mL	Reinforce Adherence
400 - 999 c/mL	Resistance testing will be performed. If resistance has developed, subject must be discontinued. If resistance has not developed, consider possible discontinuation of subject, in consultation with BMS Medical Monitor, and/or reinforce adherence.
\geq 1000 c/mL	Resistance testing will be performed. Regardless of result of resistance tests, subject must be discontinued (see Section 3.5).
After Week 48	
< 200 c/mL	Reinforce Adherence
\geq 200 c/mL	Subject must be discontinued (see Section 3.5). If \geq 400 c/mL, consider the need for resistance testing, in consultation with BMS Medical Monitor.

^a When discontinuation is required or otherwise warranted and resistance results are needed, subject may continue on study medication/on study until resistance testing results are available.

5.4.1.2 *Protocol Defined Virologic Failure*

Protocol Defined Virologic Failure (PDVF) is defined by a subject meeting one of the following three criteria:

- 1) Confirmed $> 1 \log_{10}$ c/mL increase in HIV-1 RNA at anytime above nadir level where nadir is ≥ 40 c/mL
- 2) Confirmed HIV-1 RNA ≥ 400 c/mL after Week 24
- 3) Failure to suppress last HIV-1 RNA to < 400 c/mL within Week 24, 48, or 96 week snapshot window

In addition to the clinical management outlined in [section 5.4.1.1](#), samples meeting criteria for PDVF will also be sent for resistance and exploratory resistance testing.

5.4.2 *Secondary Efficacy Assessments*

5.4.2.1 *CD4+ and CD8+ T-Cells*

CD4+ and CD8+ T-cells counts and percentages will be assessed using flow cytometry. The schedule of assessments is provided in [Section 5.1](#) (Flow Chart/Time and Events Schedule). Procedures for samples collection and processing are provided in the central clinical laboratory manual.

5.4.2.2 *Drug Resistance Testing*

Plasma samples for viral drug resistance testing will be collected at Screening for all subjects and the HIV-1 drug resistance genotype will be analyzed to rule out resistance to any component of the study regimen or specific resistance mutations as outlined in [Section 3.3.2](#), Exclusionary Criteria. At subsequent visits, samples for emergent drug resistance testing (both genotypic and phenotypic) will be collected and stored to be as outlined in [Section 5.4.1](#).

5.5 *Pharmacokinetic Assessments*

It is extremely important to record the exact dose and time of the dose(s) taken the day prior to the visit/collection, and the exact date and time of the sample collection, even if drawn slightly off-schedule.

5.5.1 *Intensive Pharmacokinetic Assessment*

A subset of subjects (about 12 subjects per treatment group) will participate in an optional Intensive PK assessment at Week 2 (window Day 12-16).

Intensive PK samples collected in this study will provide for the assessment of BMS-955176, ATV, RTV, and DTG to support the secondary and exploratory objectives (to characterize the PK of BMS-955176, DTG, and ATV (with or without RTV) when given in combination, and to compare steady-state exposures of DTG when co-administered with BMS-955176 and ATV/RTV to DTG when co-administered with TDF and ATV/RTV).

Intensive PK sampling begins with a morning pre-dose (0 hour) sampling, ie, prior to the administration of the morning doses of the study drugs on the day of the visit. The sampling

should also begin 24 hours after the morning doses of the study drugs that were taken the day prior to the visit.

The subsequent 11 time points include samplings through Hour 12, with the last sample collected at Hour 24. The subject will either stay overnight or will return to the clinic so that the final sample can be collected at Hour 24.

It is critical to capture the exact date and time of each PK sample collection, even if drawn slightly off-schedule. There is no specified collection window end for which any one time point should be abandoned as the schedule progresses. If a sample collection time point is missed/late and the next collection time point has not yet been reached, collect the missed time point, and record the exact time of that collection, then get back on track for the next time point/on-time collection.

Table 5.5.1-1 lists the sampling schedule to be followed for the assessment of intensive pharmacokinetics. Further details of PK blood collection and sample processing will be provided in the central clinical laboratory manual.

Table 5.5.1-1: AI468048 Intensive Pharmacokinetic Sampling Schedule at Week 2

	Time (Event)	Time (Relative to Dosing) Hour: Min	PK Blood Sample
Study Week 2 (window Day 12-16)	0 (morning pre-dose)	00:00	X
	1 Hr	01:00	X
	2 Hr	02:00	X
	2.5 Hr	02:30	X
	3 Hr	03:00	X
	4 Hr	04:00	X
	4.5 Hr	04:30	X
	5 Hr	05:00	X
	6 Hr	06:00	X
	8 Hr	08:00	X
	12 Hr	12:00	X
	24 hr (morning pre-dose)	24:00	X

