1.4.1.2 Nonclinical studies

Nonclinical Pharmacology and Microbiology

BMS-955176 specifically inhibits HIV-1 protease cleavage at the CA(p24)/SP1 junction within the Gag protein in both HIV-1-infected cells and purified HIV-1 Gag virus-like particles (VLPs). Radiolabeled BMS-955176 specifically binds to purified HIV-1 Gag VLPs, and its binding is dose-dependently inhibited by related MIs and is reversible. BMS-955176 does not directly inhibit HIV-1 protease nor bind to a small HIV-1 protease peptide substrate. These results indicate that BMS-955176 inhibits late in the HIV-1 life cycle by specific binding to immature capsid structures at or near the CA(p24)/SP1 junction, thereby inhibiting cleavage at that particular site. In cell culture, the range of values for the concentration producing 50% effect (EC50) of BMS-955176 against 7 common laboratory strains of HIV-1 was 1.6 to 10.5 nM (mean = 6.0 ± 3.5 nM). Using a reverse transcriptase readout, a phenotyping analysis of 93 subtype B viruses whose genotypes are representative of 96% of the diversity (found in the Los Alamos National Laboratory [LANL] database) in Gag sequences indicates that the mean EC50 of this cohort was 2.7 ± 1.9 nM, with a median value of 2.2 nM and a range between 0.6 to 12 nM. A similar analysis of 23 isolates of subtype C viruses found a mean EC50 of 6.1 ± 3.1 nM, a median value of 5.6 nM, and a range from 2.5 to 16 nM. When evaluated against clinical isolates in peripheral blood mononuclear cells (PBMCs), BMS-955176 exhibited a mean EC50 of 24 ± 24 nM against a cohort (N = 22) of subtype B viruses. Activity was also observed against viruses from subtypes A, C, D, F, and G, with average EC50 values for 96% of tested isolates (N = 41) between 5.9 and 87 nM. Clinical isolates from the CRF01_AE subtype were approximately 2- to 3-fold less susceptible to BMS-955176 (average EC50 77 nM, N = 7) viruses. BMS-955176 was active against 1 of 3 human immunodeficiency virus type-2 (HIV-2) isolates (EC50 = 15 nM). BMS-955176 retains complete activity against reverse transcriptase (RT), protease, and integrase inhibitor-resistant viruses, with EC50 values similar to wild-type (wt) viruses, while the potency of currently approved nucleotide/nucleoside reverse transcriptase inhibitors (NRTIs), non-nucleoside reverse transcriptase inhibitors (NNRTIs), protease inhibitors (PIs), and integrase inhibitors (INIs) was undiminished when tested against viruses with reduced susceptibility to BMS-955176. BMS-955176 maintained activity against a panel of PI-resistant isolates from PI-treated subjects harboring a variety of major and minor PI-resistance determinants in both protease and Gag.^{27,28} Protein binding to 100% human serum (HS) was 86%, and in the presence of 40% HS supplemented with additional human serum albumin (HuSA) to match physiologic concentrations, BMS-955176 exhibited an approximately 4-fold reduction of antiviral activity. Selection for resistance to BMS-955176 in cell culture identified changes that map to amino acids adjacent to the CA(p24)/SP1 cleavage site. These include an amino acid substitution of A364V or a combination of V362I with secondary changes (V370A, A374P or I376V). In vitro, virus with the A364V change exhibited a drastic loss of susceptibility to BMS-955176 (>100-fold), while the V362I plus secondary change-containing viruses were

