8.3.2 Secondary Endpoint(s)

- The antiviral efficacy will be determined by the proportion of subjects with plasma HIV-1 RNA < 40 c/mL at Weeks 48 and 96 using the FDA snapshot algorithm
- The antiviral efficacy will also be assessed by the proportion of subjects with plasma HIV-1 RNA < 200 c/mL at Weeks 24, 48 and 96 using the FDA snapshot algorithm approach with positive response defined as HIV-1 RNA < 200 c/mL
- The emergence of HIV drug resistance among samples sent for drug resistance testing will be assessed using the most recent version of the IAS-USA list of HIV-1 drug resistance mutations
- Changes from baseline in \log_{10} HIV-1 RNA and in CD4+ T-cell counts, and changes in the percentage of CD4+ T-cells will be assessed using on-treatment laboratory results, and pre-specified visit windows
- The frequency of SAEs and AEs leading to discontinuation (DC) will be tabulated directly from the case report forms (CRFs). The summary will count the number of subjects that have at least one event
- The occurrence of new AIDS defining events (CDC Class C events) will be tabulated from the CRFs. The summary will count the number of subjects that have at least one event
- The steady-state plasma PK of BMS-955176 will be assessed using the intensive PK data, collected at Week 2 from a subset of subjects

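### The virologic failure definition omits a confirmed early rebound after suppression below 40 c/mL when the subject leaves before the Week 24 window or is below 400 c/mL in it

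*Protocol*

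**What the plan says.** All references are to Revised Protocol 01.

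Section 5.4.1.2 lists three ways to be PDVF. Criterion 1 is a confirmed rise of more than 1 log10 over the nadir, limited to subjects whose nadir is 40 c/mL or higher. Criterion 2 is "Confirmed HIV-1 RNA ≥ 400 c/mL after Week 24". Criterion 3 is a last value that is not below 400 c/mL in the Week 24, 48 or 96 snapshot window. The section then states that "samples meeting criteria for PDVF will also be sent for resistance and exploratory resistance testing".

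Section 5.4.1.1 has a separate rule for repeat testing. Its first trigger is a value of at least "40 c/mL if prior suppression" below that level had been reached, so rebound after suppression is a recognised event. In Table 5.4.1.1-1, a confirmed value of 400 c/mL or more from Day 1 through Week 24 leads only to "Consider the need for resistance testing, in consultation with BMS Medical Monitor", with possible discontinuation raised in the same row. Section 5.9 adds that on-treatment resistance samples are tested when judged clinically relevant.

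The secondary objective on emergent resistance (Section 1.3.2) concerns the samples selected under Section 5.4.1. Section 8.3.2 says that emergence "will be assessed using the most recent version of the IAS-USA list of HIV-1 drug resistance mutations". Section 8.4.2.2 tabulates, by arm, all newly emergent substitutions and the newly emergent phenotypic profile, and refers to no list.

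**The concern.** The three criteria leave a hole between them. Criterion 1 excludes anyone who has been below 40 c/mL, criterion 2 does not start until after Week 24, and criterion 3 needs a high value in a window. The subject who falls through responded well at first and then lost control of the virus early. That is a plausible carrier of emergent resistance, which Sections 1.1.3 and 1.5 name as the risk of Arms 3 and 4.

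The practical effect is on which samples are tested. PDVF samples go for testing by rule. Outside PDVF, before Week 24, the decision rests on judgement by people who know the treatment arm. Section 8.4.2.2 speaks of all on-treatment isolates, but a table of results can contain only the isolates that were tested.

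Two wording conflicts bear on the same endpoint. Section 8.3.2 reads resistance from a published list, while Section 8.4.2.2 does not. The after-Week-48 row of Table 5.4.1.1-1 asks only that testing be considered at 400 c/mL or more, while a confirmed value at that level is PDVF by criterion 2 and is sent for testing.

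**Working it through.** **The plan's own figure.** Section 8.1 expects about 80% response with 40 subjects per arm and gives an exact 95% interval of roughly 64% to 91%. For 32/40 the Clopper-Pearson interval is 64.4% to 90.9%, so the figure reproduces. The point does not depend on it, but it sets the scale: 40 − 32 = 8 expected non-responders per arm, for any reason.

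**The criteria applied literally.** Each rebound below is taken as confirmed about three weeks after the first high value.

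- A. Nadir 45, rebound to 460 at Week 12. log10(460/45) = 1.01, which exceeds 1: PDVF by criterion 1.
- B. Nadir below 40 at Week 8, rebound to 50,000 at Week 12, stops before Week 24. Criterion 1 is barred by the nadir, criterion 2 by the date, and criterion 3 has no value in a window: **not PDVF**.
- C. As B, but stays on study with 50,000 at Week 24: PDVF by criterion 3.
- D. Nadir below 40, rebound to 5,000 at Week 12, then 350 at Week 24: **not PDVF**.
- E. Nadir below 40, rebound to 5,000 at Week 12, suppressed again at Week 24: **not PDVF**.
- G. Nadir below 40, rebound to 5,000 at Week 32: PDVF by criterion 2.

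A and B set side by side show the inconsistency: a tenfold rise to 460 counts, and a rise from below 40 to 50,000 does not.

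**After an added criterion** (confirmed value of 400 c/mL or more at any time after a value below 40): B, D and E become PDVF, and A, C and G stay PDVF. The threshold fits criterion 1, since 10 × 40 = 400. A confirmed rebound to 300 at Week 60 is outside PDVF both before and after the change.

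**How often.** The protocol gives no rate of early rebound, so the share p of subjects on the uncaptured path is an assumption. The expected number per arm is 40p, and the chance of at least one in an arm is 1 − (1 − p)^40.

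- p = 1%: 0.4 expected; 33%
- p = 2.5%: 1 expected; 64%
- p = 5%: 2 expected; 87%
- p = 10%: 4 expected; 98.5%

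**The case against.** The strongest reply is that the hole is narrow and that untested is not the same as missed. Much of this stands. Criterion 3 catches an early rebound that is still at 400 c/mL or more in the Week 24 window, and criterion 2 catches confirmed values at that level afterwards. A reader might infer that PDVF ignores all rebound before Week 24; trajectory C shows that it does not. Before Week 24 the medical monitor must at least be consulted, the table's footnote lets a subject stay on study until resistance results arrive, and samples are stored at the scheduled visits and at early termination. Some of these subjects will be tested.

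A reader might also infer that resistance to BMS-955176 would be scored as absent, because Section 8.3.2 uses a published list while Section 1.4.1.2 places the drug's resistance in Gag ("These include an amino acid substitution of A364V or a combination of V362I with secondary changes"). The documents do not support that. Section 8.4.2.2 tabulates every newly emergent substitution and the phenotype, Gag sequencing and PhenoSense Gag samples are collected on treatment, and the list's content cannot be checked here. Phenotypic cut-offs and scoring rules may properly sit in the SAP.

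Nor do the documents support a stated share of failures escaping testing, or a bias of known direction between arms. The rule is the same in every arm, and no between-arm test of resistance is planned.

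Finally, criterion 3 could be read to count a subject with no value in the window as having failed to suppress. The text does not say so, and that reading would still leave D and E uncaptured.

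What the reply does not remove is trajectories B, D and E. For them, a rule that is mandatory elsewhere becomes optional.

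**Conclusion.** The gap is real but limited. It affects subjects who reach below 40 c/mL, have a confirmed rebound to 400 c/mL or more before Week 24, and then either discontinue before the Week 24 snapshot window or are below 400 c/mL in it. Because PDVF decides who must be tested, the secondary resistance endpoint can miss some of these early rebounders. This is a stated rule that misclassifies, not detail left for later.

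The number affected cannot be derived from the protocol. At an assumed 1% to 10% it is 0.4 to 4 subjects per arm, against about 8 expected non-responders, and those figures count subjects outside PDVF before allowing for any discretionary testing. The conclusion rests on reading criterion 3 as needing a measured value in the window. The window's length in days is not given in the protocol, so a stop shortly before Week 24 might still fall inside it.

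The two wording conflicts are genuine, but they call for reconciliation only.

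**What to change.** Add a fourth criterion to Section 5.4.1.2: confirmed HIV-1 RNA of 400 c/mL or more at any time after a value below 40 c/mL. State that it serves classification and resistance testing only and creates no new stopping rule.

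Align Section 8.3.2 with Section 8.4.2.2, so that newly emergent Gag changes and the phenotypic profile are reported under the resistance endpoint alongside the published list. Do not confine the Gag changes to a fixed set: Section 1.4.1.2 gives its cell-culture changes as examples, and Section 1.5 says that analysis of clinical emergent changes was still under way.

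Reconcile the after-Week-48 row of Table 5.4.1.1-1 with criterion 2 and the statement that PDVF samples are sent for testing.

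The cost is a few extra assays on samples that Table 5.1-2 already has collected and stored at each scheduled visit from Week 4 and at early termination, plus wording in three places. No visit, sample or subject is added.
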